In order to investigate the relationship between steady-state trough concentrations of everolimus in adjuvant renal cancer patients and drug toxicity, we will collect specimens to study the incidence of lymphopenia, infection, thrombocytopenia, hyperglycemia, hypercholesterolemia, hypertriglyceridemia, stomatitis, creatinine elevation, and non-infectious pneumonitis as pharmacodynamic markers of everolimus exposure. Blood sampling for pre-dose trough levels of everolimus will be obtained after registration, but prior to treatment; at the beginning of Cycles 2 and 3; and at the time the patient is removed from protocol treatment. Everolimus whole-blood concentrations will be determined via high-performance liquid chromatography/mass spectroscopy assay. Relationships between everolimus steady-state  $C_{min}$  and the incidence of specific toxicities will be explored.

Trough levels of everolimus in post-nephrectomy renal carcinoma patients will correlate with toxicity and yield an upper threshold level that can be used in developing a therapeutic range for everolimus in the adjuvant population.

Inclusion of Women and Minorities:

This study was designed to include women and minorities, but was not designed to measure differences of intervention effects. The anticipated accrual in the ethnicity/race and sex categories is shown in the table below. Both men and women of all races and ethnic groups are eligible for this study.

Ethnic Category	Females	Males	Total
Hispanic or Latino	55	89	144
Not Hispanic or Latino	436	957	1393
Total Ethnic	491	1046	1537
Racial Category			
American Indian or Alaskan Native	1	4	5
Asian	10	42	52
Black or African American	29	42	71
Native Hawaiian or other Pacific Islander	0	0	0
White	451	958	1409
Racial Category: Total of all Subjects	491	1046	1537

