## 7.2 Treatment Schedule

All patients will be randomized to receive either everolimus or placebo daily for nine, six week cycles.

AGENT	DOSE	ROUTE	DAYS	DURATION
Everolimus or Matched Placebo	10 mg (two 5 mg Tablets)	Oral	Every Day	378 days (54 weeks)

\* Everolimus (or matched placebo) tablets are supplied as 5 mg tablets.

Everolimus must be administered orally, once daily preferably in the morning with a glass of water and no more than a light fat-free meal. Tablets must be swallowed whole with a glass of water. The tablets must not be chewed or crushed, and grapefruit or citrus juices should be avoided.

A cycle of treatment is six weeks. Assessment for the primary endpoint (recurrence) must occur after every three cycles (18 weeks) for 54 weeks, then every six months for two years, and then annually thereafter until recurrence, death, or 10 years after registration, whichever comes first (regardless whether patient is still on active protocol treatment). Recurrence assessments consist of physical exams and CT scans.

Radiographic assessment for pneumonitis must be undertaken as per [Section 8.4c](#).

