If 936 of patients randomized to this trial provide a usable tissue sample for these translational objectives, and the prevalence of the biomarker of interest is 20%, then we will have reasonable power (80%) to detect a hazard ratio of approximately 0.50 for those with a marker compared to a HR of 1.0 for those without the marker ( $1.0/0.50 = 2.00$ ). Frequency and severity of adverse events and proximity to sample collection will be correlated with steady-state  $C_{min}$ . Assuming 90% of those randomized to everolimus will submit one or more serum samples, we will have approximately 526 subjects to analyze.

Initially, correlations of adverse events and the  $C_{min}$  in closest proximity to the adverse event will be explored in a manner analogous to multiple t-tests. Logistic regression modeling will be used to assess whether  $C_{min}$  is a predictor for the presence of the adverse events after adjusting for other patient and disease covariates. Proportional odds (PO) models may be used to model severity of an adverse event in ordinal categories, if the PO modeling assumption is supported by the data.

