#### 11.5 Pharmacokinetic Analysis of Blood Samples

For the pharmacokinetic analysis of blood samples, we will use blood samples that were collected at Week 7 or Week 13 and the patient must have been randomized to the everolimus arm and be receiving protocol treatment at the time of the blood draw. At the time of the on-study analysis in the winter of 2014, there were 83 patients with one blood draw and 165 with two for a total of 248 patients. For those with two on-treatment measurements, the average of the two will be used for analysis to reduce measurement error bias.

The purpose of the analysis is to correlate everolimus blood concentrations from early blood draws with the experience of adverse events by the patients, both in terms of general grades of toxicities but also by specific adverse events that have been more frequently reported on the everolimus arm. The following calculations assume a PK analysis will be conducted prior to accrual completion in order to gain insight into the relationship between blood levels of the study drug and adverse events. We anticipate there will be more samples to evaluate later in the trial and so effect sizes will be smaller with larger sample sizes.

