### 2. Whole Blood

Five mL of venous blood will be collected in a purple-top EDTA tube immediately prior to Cycles 1-3 and at the time the patient is removed from protocol treatment. **Prior to Cycles 1-3, patients must be instructed not to take their morning everolimus dose until after the samples have been obtained.** These specimens must be shipped within 28 days after obtaining to Lab #201. These specimens will be banked until funding is obtained to perform translational medicine studies which will include determining the steady-state everolimus trough levels.

c. Plasma and Whole Blood Specimen Collection Instructions:

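### Section 11.4 does not say which draws count as steady-state Cmin, and Section 11.5 does not exclude levels taken during or just after a hold or dose change

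*Combined protocol and SAP*

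**What the plan says.** Objective 1.3b and the pharmacodynamic part of Section 2.0 name the steady-state trough as the exposure to be related to toxicity.

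Section 11.4 plans correlations between adverse events and the Cmin "in closest proximity to the adverse event will be explored in a manner analogous to multiple t-tests". It states no draw window and no on-treatment condition, and its sample count takes in any everolimus patient who submits at least one sample.

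Section 15.2b fixes the draws, the last of them when study treatment ends: "Five mL of venous blood will be collected in a purple-top EDTA tube immediately prior to Cycles 1-3 and at the time the patient is". The first of these precedes any drug. The specimen footnote to the Section 9.0 calendar asks for the removal sample at whatever point removal happens, and requires all specimens to be taken before that day's dose.

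Section 11.5 is narrower: "we will use blood samples that were collected at Week 7 or Week 13", the patient must be on the everolimus arm, and must "be receiving protocol treatment at the time of the blood draw". On numbers, "there were 83 patients with one blood draw and 165 with two for a total of 248 patients". On repeat draws, "For those with two on-treatment measurements, the average of the two will be used for analysis". Patients already on a reduced dose are analysed twice, once on the raw level and once standardised for dose. No minimum time at a stable dose is given.

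**The concern.** Everolimus is held or reduced because of toxicity, so a level taken during or after a hold is low for a reason tied to the event under study. If such a level stands in for the patient's exposure, patients with events look less exposed than they were. That is not random noise: it pulls the exposure–toxicity association downward.

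The route is most direct in Section 11.4. The event that leads to removal often lies close in time to the removal draw, so the nearest-level rule can select the washed-out sample. The table in Section 11.5 puts refusal or toxicity before 12 months at 52% of the everolimus arm, so early removal is common. The documents do not say how many of those patients had been off drug when the removal sample was drawn.

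**Working it through.** **Which draws qualify**

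| Draw | Section 11.4 as written | Section 11.5 |
|---|---|---|
| Before Cycle 1 (no drug) | not excluded | excluded |
| Start of Cycles 2 and 3 (Weeks 7 and 13) | eligible | eligible if on protocol treatment |
| At removal | eligible, any time since last dose | excluded |

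With draws at about 0 and 6 completed weeks, the midpoint is (0 + 6)/2 = 3 weeks. Read literally, the nearest-level rule ties an event in the first three weeks to the drug-free sample.

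**Washout.** Half-life about 30 h (Section 3.1b), simple exponential decline assumed. Fraction left after d further days without drug = 0.5^(24d/30).

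| Days off drug | 1 | 2 | 5 | 7 | 14 | 21 |
|---|---|---|---|---|---|---|
| Level left | 57% | 33% | 6.3% | 2.1% | 0.04% | 0.0009% |

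Sections 7.6c and 8.2e remove a patient once treatment is held more than 21 days (pneumonitis) or 28 days (other reasons). A removal sample taken under that criterion therefore contains essentially no drug. A patient held for a shorter time is still on study and, on one reading, still receiving protocol treatment at Week 7 or 13.

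**Just after a hold and reduction.** Most reductions in Section 8.4 follow an interruption. Write r = 0.5^(24/30) = 0.574 for the daily carry-over. After a 7-day hold from 10 mg and 2 days back at 5 mg, the trough relative to its new steady state is (1 − r²) + 2r⁹ = 0.670 + 0.014 = 0.68. The recovering level is too low, and dividing by the current dose does not correct it.

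**Averaging across a dose change.** Steady-state troughs in relative units are 10r/(1 − r) = 13.49 at 10 mg daily and 6.75 at 5 mg daily. If Week 7 is at 10 mg and Week 13 at 5 mg, the mean is 10.12. The true value per mg is 1.349. The mean divided by 10 is 1.012 (0.75 times true); divided by 5 it is 2.024 (1.50 times true). Standardising each draw to its own dose first gives 1.349 both times.

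**Every-other-day level (Section 8.3).** At 5 mg every 48 h the level is 5r²/(1 − r²) = 2.46 at 48 h and 5r/(1 − r²) = 4.29 at 24 h. Against 6.75 for 5 mg daily these are 0.36 and 0.64, where average dose predicts 0.50. A standardised value is therefore 0.73 or 1.27 times true, depending on the day drawn.

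**Power in Section 11.5.** 83 + 165 = 248 patients, or 62 per quartile. The stated detectable odds ratios for prevalences of 10% to 50% are 6.5, 3.6, 3.0, 2.7 and 2.7. Taking prevalence as the mean of the two quartiles and using the arcsine two-proportion formula at two-sided 0.05, I get 6.67, 3.72, 3.07, 2.83 and 2.77. Power at the stated values is 0.792, 0.782, 0.784, 0.763 and 0.781. The 40% column is the one that does not reproduce; with 65 per quartile all five fit. The point does not depend on that gap.

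Suppose a share f of the lowest- and highest-quartile values carries no exposure information, so the risk difference shrinks by (1 − f). Compare this with dropping the same share of patients, so n becomes 62(1 − f):

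| f (assumed) | Power, values kept | Power, values dropped |
|---|---|---|
| 0 | 0.76–0.79 | 0.76–0.79 |
| 5% | 0.72–0.74 | 0.74–0.77 |
| 10% | 0.67–0.69 | 0.72–0.75 |
| 20% | 0.57–0.59 | 0.67–0.70 |

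Keeping uninformative values costs more power than removing them.

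**The case against.** Several stronger readings are tempting, and the documents do not support them.

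- *That Section 11.5 treats every draw as a steady-state trough.* It does not. It speaks of blood concentrations from early draws, and its on-treatment condition removes the pre-treatment and removal samples. The drug-free and removal-draw problem belongs to Section 11.4.
- *That newly reduced doses push standardised levels into the top quartile.* Section 8.4 mostly interrupts drug before restarting lower, so the usual error is a low value. A direct step-down appears for Grade 2 pneumonitis.
- *That late events in patients who finish treatment are paired with washed-out levels.* A completer's removal draw need not be washed out. The concern is removal after a hold.
- *That many draws are mid-interval.* Section 9.0 requires sampling before the daily dose. Section 7.2 only prefers morning dosing ("Everolimus must be administered orally, once daily preferably in the morning with a glass of water"), so an evening doser sampled in the morning remains possible, but no share is given. The Intake Calendar asks for tablets per day, not clock time; the Treatment Form and specimen-tracking fields cannot be seen.
- *That a planned threshold analysis is distorted.* Section 2.0 expects trough levels to "yield an upper threshold level that can be used in developing a therapeutic range for everolimus in the adjuvant population", but neither Section 11.4 nor 11.5 says how a threshold would be derived.

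It is also fair to say that a sensible analyst would not call a drug-free sample steady state, that averaging softens one bad draw in the 165 patients with two (while giving each two chances of a bad draw), and that objective 1.3b only banks specimens for future study. These points limit the stakes. They do not supply the missing rule, and the removal-sample gap does not depend on an unreasonable reading.

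**Conclusion.** The point holds as a gap in sample selection. Section 11.4 lets any scheduled draw stand for steady-state Cmin, including a removal sample with about 2% of the level left after 7 days off drug and practically none after 21. The expected direction is an exposure–toxicity association that is too weak. Section 11.5 avoids the two worst samples, but leaves holds, recent dose changes, averaging across doses and the 48-hour interval unaddressed.

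The per-sample figures rest on the stated half-life, one-compartment first-order decline and dose-proportional levels. The overall effect cannot be stated, because the documents give neither the share of affected samples nor the between-patient spread; the power ranges illustrate assumed shares and treat the error as uninformative rather than toxicity-related. The primary endpoint is not touched.

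**What to change.** Change the analysis rules only; they can be applied to banked samples.

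- In Sections 11.4 and 11.5, treat a level as evaluable only if drawn on treatment after at least 7 days of uninterrupted dosing at one dose level, per the Intake Calendar or Treatment Form. After 7 days about 2% of any earlier imbalance remains.
- Exclude the pre-treatment sample. Use a removal sample only if it meets the same rule.
- Standardise each draw to its own dose before averaging, and handle every-other-day dosing separately.
- Report the all-samples analysis as a sensitivity analysis. Where dosing time is known, add one limited to morning dosers.

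Cost: SAP wording and work on dosing records. Section 7.4 keeps the calendar in the clinic chart and lets some sites use other records, so queries may be needed if the Treatment Form lacks hold dates. A time-of-last-dose field cannot be recovered for samples already drawn. Some samples become non-evaluable; if 10% of patients were lost (assumed), the detectable odds ratio by the arcsine method would rise from 3.07 to 3.27 at 30% prevalence and from 6.67 to 7.64 at 10%. Exclusions may themselves be related to toxicity, which is why the all-samples analysis stays.

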#### Most Prevalent Grade 2-4 Adverse Events in the Everolimus Arm of EVEREST

Among all Randomized Patients on the Everolimus Arm Who Received Any Study Drug

Toxicity	% of Evaluable with Grade 2-4
High Cholesterol	10%
Fatigue	19%
Hyperglycemia	14%
Hypertriglyceridemia	27%
Oral mucositis	35%
Rash	14%
Composite Endpoints	
Any Toxicity Grade 2-4	87%
Any Toxicity Grade 3-4	46%
Refusal/Tox within first 3 months	25%
Refusal/Tox within first 6 months	41%
Refusal/Tox prior to 12 months	52%

In order to simplify power calculations related to everolimus blood concentrations, we will assume the distribution of values will be divided into quartiles. The following table indicates the minimally detectable odds ratio that could be detected between the lowest and highest quartile in terms of predicting an adverse event. A range of prevalences are illustrated below to show how the effect size changes with the prevalence of the adverse event.

Minimally Detectable Odds Ratio for Highest versus Lowest Quartile of everolimus in the blood, assuming 80% Statistical Power and a Two-sided Alpha=0.05.

	Prevalence of Adverse Event Endpoint				
	10%	20%	30%	40%	50%

Q4 vs. Q1 of everolimus concentration	6.5	3.6	3.0	2.7	2.7
---------------------------------------	-----	-----	-----	-----	-----

An individual adverse event that is only reported by 10% of patients who receive everolimus will need to have a very strong association with concentration of everolimus in the blood (odds ratio 6.5 between highest and lowest concentration) in order to be detected as a significant association. An association of any Grade 3-4 toxicity only needs to be in the range of an odds ratio of 2.7 to be detectable.

For patients who have had a dose reduction of protocol therapy at the time of their blood draw, we will handle this in two ways. First, we will just analyze the everolimus level as it appears in the blood and ignore the dose received, and the second approach will standardize the amount of everolimus in the blood conditional on the dose of drug taken.

Logistic regression will be used to model adverse event outcomes with everolimus blood concentration as a predictor, adjusting for other stratification factors and age, gender and race.

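### The exploratory PK-toxicity analysis does not require the adverse event to follow the blood draw, so its raw-level version can understate an exposure-toxicity link

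*Combined protocol and SAP*

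**What the plan says.** Section 11.5 defines the exposure: "we will use blood samples that were collected at Week 7 or Week 13", from everolimus-arm patients who must "be receiving protocol treatment at the time of the blood draw". When a patient has both samples, they are averaged. The analysis set in winter 2014 was 248 patients, 83 with one draw and 165 with two. The stated purpose is to "correlate everolimus blood concentrations from early blood draws with the experience of adverse events by the patients", with no time window for the outcome and no exclusion of patients who had the event before the draw.

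The power paragraph compares the "lowest and highest quartile in terms of predicting an adverse event", and logistic regression takes concentration as the predictor. For patients on a reduced dose at the draw, two analyses are planned. In one, "First, we will just analyze the everolimus level as it appears in the blood and ignore the dose received". In the other, "the second approach will standardize the amount of everolimus in the blood conditional on the dose of drug taken". Neither is named as the lead. On power, the section says "An association of any Grade 3-4 toxicity only needs to be in the range of an odds ratio of 2.7 to be detectable".

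Section 11.4 links each event to the trough closest in time, which fixes nearness but not order.

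Sections 8.2-8.4 set the dose rules. Most Grade 3 non-hematological events, and intolerable Grade 2 events that return, lead to a lower dose level, and re-escalation is barred. The first step down in Section 8.3 is from 10 mg to 5 mg daily. Section 9.0 requires toxicity assessment every week of Cycle 1.

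**The concern.** Six weeks of adverse events can come before the first usable level. A patient whose early event caused a dose reduction then contributes a low level together with a positive outcome. In the raw-level analysis this moves event patients towards the bottom quartile and works against a true positive association. Even where the dose did not change, an event before the draw is paired with a level that the patient may not have had when it occurred, so the result cannot be read as prediction.

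Section 2.0 hopes that trough levels will yield an upper threshold for a therapeutic range. An understated or wrongly ordered association is a weak basis for that. Nothing confirmatory depends on it.

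**Working it through.** **Plan's own figure.** Inputs from Section 11.5: 248 / 4 = 62 patients per quartile, two-sided 0.05, 80% power. With p1 and p4 the event risks in the bottom and top quartiles, and their mean set to the stated prevalence:

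power = Φ( |2·arcsin√p4 − 2·arcsin√p1| / √(2/62) − 1.96 )

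Solving for 80% power at prevalences of 10/20/30/40/50% gives odds ratios of 6.7/3.7/3.1/2.8/2.8, against the plan's 6.5/3.6/3.0/2.7/2.7. An unpooled-variance version with risk log-linear across the four quartiles gives 6.39/3.62/3.00/2.77/2.71. The table reproduces, so its arithmetic is not in question.

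**Effect of event order on the raw analysis.** From the documents: any Grade 3-4 toxicity 46%, halving of dose at the first reduction, 165 of 248 patients with two draws. Assumed: true odds ratio 2.7, log-level SD 0.5 between and 0.2 within patients, level proportional to dose, event timing independent of level, and the shares reduced. The documents give no count of reductions before Week 7 or Week 13.

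Event patients: 0.46 × 248 = 114. Share halved before the draw:

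- 30% of events early × 25% of those halved = 7.5%, about 9 patients (114 × 0.075 = 8.6).
- 60% early × 25% halved = 15%, about 17 patients (114 × 0.15 = 17.1).

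Simulated raw-level odds ratio:

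| Condition | 7.5% halved | 15% halved |
|---|---|---|
| All reductions before both draws, no other reductions | 2.1 | 1.65 |
| Half of reductions in two-draw patients fall between draws | 2.2 | 1.8 |
| All reductions before both draws, 5% of never-event patients also reduced | 2.4 | 1.9 |
| All reductions before both draws, 10% of never-event patients also reduced | 2.8 | 2.15 |

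Changing the between-patient SD from 0.35 to 0.7 moves the first row to 2.0-2.2 and 1.5-1.8.

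**Power for the first row.** With 62 per quartile, mean risk 46% and a pooled two-proportion test:

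- Odds ratio 2.7: risks 0.339 and 0.581, power about 78%.
- Odds ratio 2.1: risks 0.369 and 0.551, power about 53%.
- Odds ratio 1.65: risks 0.398 and 0.522, power about 28%.

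**Dose standardisation.** Under proportionality the standardised level recovers 2.7 by construction. The order of operations matters. Take a sample of L at 10 mg and one of L/2 at 5 mg. Each divided by its own dose gives L/10 both times, mean 0.1L. Averaging first gives 0.75L, which becomes 0.15L if divided by 5 mg and 0.075L if divided by 10 mg.

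**Cost of counting only after-draw events.** Let s be the share of the 114 events that first occur after the draw (assumed). At risk = 248 − 114(1 − s); events = 114s; arcsine formula with a quarter of those at risk per group:

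| s | At risk | Events | Detectable odds ratio |
|---|---|---|---|
| 25% | 162 | 29 | 5.9 |
| 50% | 191 | 57 | 3.6 |
| 75% | 219 | 86 | 3.05 |

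This applies the 46% seen in all treated everolimus patients to the 248, which is also an assumption.

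**The case against.** The strongest reply is that the plan already sees dose reductions and answers them with the standardised analysis, which closes the path from event to level to the extent that levels are proportional to dose. A marked difference between the two planned results would itself expose the problem. That stands, and it keeps the concern to one of two analyses. It does not settle which result is reported as the finding, how samples taken at different doses are averaged, or whether the event came after the level.

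Second, the mechanism is weak for part of the endpoint list. Section 8.4 sends Grade 2-3 hyperlipidemia to medical treatment, recommends no dose change for anemia, and keeps the dose for tolerable or first intolerable Grade 2 events and a first Grade 3 neutropenia. Grade 4 non-hematological events stop the drug, and patients off treatment at the draw are not analysed. This stands too. The figures above apply to the Grade 3-4 composite and not to every event.

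Third, a time-ordered analysis is no cure-all. Under the same assumptions its power at 2.7 is about 70% with 30% of events early and about 52% with 60% early. On raw levels it reads 3.1-3.6 if 5-10% of never-event patients are reduced. If higher levels bring earlier events, excluding early-event patients pulls the estimate down, to about 2.6-2.3 in an illustrative frailty run at a Week 7 draw. It therefore belongs beside the standardised analysis, not in its place.

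A reader might also infer that "Refusal/Tox within first 3 months" is a PK outcome because it is listed among the composites. Section 11.5 describes the outcomes as toxicity grades and specific events and never says that stopping treatment is modelled, so no point is made of it.

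**Conclusion.** The gap is real and minor. Sections 11.4-11.5 set no event order, and the raw-level analysis can understate the association. Its size rests on assumed shares: from 2.7 down to about 2.1-1.65 if 7.5-15% of event patients are halved before both draws and nobody else is reduced, and to about 2.2-1.8 if half of the two-draw reductions fall between draws. If 10% of never-event patients are also reduced, the understatement disappears in the smaller scenario (2.8) and is about halved in the larger (2.15).

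A reader might infer that the analysis would hide or reverse a true link. The documents do not support that. With the spread of levels assumed here, a reading near 1.0 needs about 30% of all event patients halved before the draw, and a reading below 1 needs about a third, with no other reductions. Nor is the stated detectable odds ratio of 2.7 wrong; it describes an all-events comparison. The analysis is exploratory, and recurrence-free survival and the between-arm toxicity comparison are untouched.

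**What to change.** 1. In Section 11.5, name the dose-standardised analysis as the lead for the all-events association. Divide each sample by its own dose before averaging, and state the dose figure used for the alternate-day level in Section 8.3. Label the raw-level all-events result descriptive.

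2. For the event models in Sections 11.4 and 11.5, add a time-ordered analysis on both standardised and raw levels. Count only events with onset or worsening after the draw that supplies the level, and exclude patients who already had that event. State how a laboratory event first found at the draw visit is classed. Use the word *predict* only if this analysis supports it.

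3. Limit the 2.7 statement to the all-events analysis. Say that the time-ordered one has fewer events and a larger detectable odds ratio (about 3.05 to 5.9 if 75% down to 25% of Grade 3-4 events first occur after the draw, an assumption), and that excluding early-event patients may itself pull the estimate down.

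The cost is SAP wording and a before/after filter. Section 15.2 places the draws immediately before Cycles 2 and 3, and Section 14.4 requires an adverse event form for each cycle, so the reporting cycle should give the order even without onset dates. The price is lower power in the added analysis and, where only one draw is used, less reduction of measurement error.
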